1. INTRODUCTION

This document outlines the statistical methods to be implemented during the analyses of data collected within the scope of Helixmith Co., Ltd. (formerly ViroMed Co., Ltd.) Protocol VMNHU-003/I [A Phase III, Double-Blind, Randomized, Placebo-Controlled, Multicenter Study to Assess the Safety and Efficacy of VM202 to Treat Chronic Nonhealing Foot Ulcers in Diabetic Patients with Concomitant Peripheral Arterial Disease (PAD)]. The purpose of this plan is to provide specific guidelines from which the analysis will proceed. Any deviations from these guidelines will be documented in the clinical study report.

Study enrollment commenced under Protocol VMNHU-003/C. There were 7 subjects enrolled under protocol version C, 5 enrolled under version E, 16 enrolled under version F, and 16 enrolled under version G; no subjects were enrolled under protocol version D, H or I.

Protocol VMNHU-003/E introduced the following changes to exclusion criteria in VMNHU-003/C:

- The study ulcer decreased by 50% or more at baseline from Screening (as assessed by comparison of post-debridement photos taken at Screening and Day 0); previously only ulcers that increased by 50% or more at baseline from Screening were excluded.
- Target ulcer located on an active (hot) Charcot foot; previously any Charcot foot was excluded.
- Body mass index (BMI) > 45 kg/m² at Screening; previously BMI > 35 kg/m² was excluded.
- All steroids except inhaled or ocular steroids; previously only high dose steroids were excluded.

Since these changes to the exclusion criteria were not expected to have a meaningful influence in favor of VM202 on the efficacy and safety parameters, no inferential analyses to account for the protocol version will be conducted. Descriptive summaries of the primary efficacy endpoint and overall adverse event rates will be produced for the subjects enrolled under different versions of the protocol.

Protocol VMNHU-003/F submitted with SAP revision C introduced the following changes to the inclusion criteria:

- the upper age limit for study participants will be raised to 80 years;
- addition of ABI > 1.4 (indicative of non-compressible vessels at the ankle) as a qualifying criterion for documented PAD;
- revision of 1 criterion for documented PAD to: history of lower extremity peripheral artery disease with previous related intervention in a leg.

Protocol VMNHU-003/G introduced the following changes to the exclusion criteria:

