3. STUDY DESIGN

This is a phase III, randomized, double-blind, placebo-controlled, multicenter, 7-month study designed to assess the safety and efficacy of intramuscular injections of VM202 in the calf of diabetic patients with chronic nonhealing foot ulcers and concomitant PAD. Subjects with confirmed PAD and diabetes aged \geq 18 years to \leq 80 years diagnosed with nonhealing foot ulcers will be screened for study eligibility after giving informed consent.

At Screening, standard of care will be initiated that will continue for the duration of the study, as follows:

- Surgical debridement of necrotic tissue or devitalized tissue
- Use of appropriate off-loading when ambulating
- Maintenance of moist wound environment

Three hundred patients (from up to 30 study centers) who meet the eligibility criteria will be randomized in a 2:1 ratio to one of two treatment groups: 200 patients with VM202 (16 mg) plus standard of care or 100 subjects with placebo plus standard of care, respectively. Safety will be monitored throughout the study by an independent Data Safety Monitoring Board (DSMB, Section 8.5).

Patients will receive intramuscular injections in the ipsilateral calf of the affected foot with the target ulcer of either VM202 or placebo on Day 0, Day 14, Day 28, and Day 42 as follows:

Treatment: Days 0, 14, 28, and 42

TREATMENT]	DOSE VM20	FINAL DOSE		
GROUP	DAY 0	DAY 14	DAY 28	DAY 42	VM202 (mg)
VM202	4	4	4	4	16
Placebo	0	0	0	0	0

0 indicates injections of Placebo

VM202 will be delivered in a solution of 0.5 mg VM202 / mL. All subjects will receive sixteen (16) 0.5-mL intramuscular injections of VM202 or placebo at each injection visit.

The schedule of study visits and the clinical parameters that will be measured at the visits are summarized in Table 1 to Table 3 below.

The subjects' target ulcer will be evaluated by photograph, surface area, depth, perimeter and volume measurements. Subjects must have a non-healing ulcer on Day 0 that meets study entry inclusion criterion # 5 and does not meet exclusion criterion #6 to be eligible for study participation. Subjects will continue to come to the clinic once a week for dressing changes and wound assessment until the ulcer has healed or study exit, whichever comes first. Measurement of the target ulcer will be performed at each follow-up visit until complete wound closure or study exit.

Further details on the study procedures and conduct are provided in the protocol.

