4. STUDY ENDPOINTS

4.1. Primary Efficacy Endpoint

The primary efficacy endpoint is the proportion of subjects with a target wound closure by the 4-month follow-up.

The statistical hypotheses for the primary efficacy endpoint are:

 H_0 : $P_t = P_c$ versus H_a : $P_t \neq P_c$

where P_t and P_c are the proportions of subjects with a target wound closure by the 4-month follow-up for the VM202 and placebo groups, respectively.

The hypothesis testing will be at a two-sided alpha of 0.05.

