6. SAMPLE SIZE CALCULATION

Based on prior VM202 studies, the percentage of subjects achieving complete wound closure by the 4-month follow-up (i.e., 4-month responder rate) for VM202 (treatment arm) is assumed to range from 50% to 60%, and that for the placebo group is assumed to range from 20% to 30%. Table 4 below summarizes the statistical power for a sample size of 200 VM202 and 100 placebo subjects based on Fisher's exact test with a two-sided significance level of 0.05 for the statistical hypothesis specified in Section 4.1.

Table 4 Statistical power by estimated responder rates for Treatment (pt) and Control (pc) arms

Pt	рc	Statistical Power
0.50	0.20	>.999
0.50	0.25	0.985
0.50	0.30	0.898
0.55	0.20	>.999
0.55	0.25	0.999
0.55	0.30	0.982
0.60	0.20	>.999
0.60	0.25	>.999
0.60	0.30	0.998

Except for the assumption of $p_t = 0.50$ and $p_c = 0.30$, the statistical power for all assumptions of p_t and p_c is > 0.95. For the assumption of $p_t = 0.50$ and $p_c = 0.30$, the statistical power is about 90%.

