9.4.1.1. Primary Analysis of the Primary Efficacy Endpoint

The primary analysis for the responder rate will be based on the ITT population.

Fisher's exact test will be used to compare the responder rate between the treatment groups. The 95% confidence interval of the responder rate of each treatment group will be derived using the binomial distribution and the 95% confidence interval of the responder rate difference will be calculated.

Subjects whose status of wound closure cannot be assessed at 4 months (e.g., due to earlier discontinuation from the study), will be considered non-responders.

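### At the 44 subjects enrolled, the primary Fisher test is valid but conservative; an exact unconditional test would recover about 0.4 to 11 points of power, depending on the unstated arm split

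*SAP*

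**What the plan says.** SAP 9.4.1.1 specifies one primary test in the ITT population: Fisher's "exact test will be used to compare the responder rate between the treatment groups". SAP 4.1 sets the level: "The hypothesis testing will be at a two-sided alpha of 0.05". Subjects whose 4-month closure status cannot be assessed count as non-responders, so dropout does not shrink the denominator.

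SAP 6 (and Protocol 6.1) gives power only for the planned trial, a "sample size of 200 VM202 and 100 placebo subjects based on Fisher's exact test with a two-sided significance level of 0.05". The assumed closure rates are 50 to 60% on VM202 and 20 to 30% on placebo. SAP 3 says patients "will be randomized in a 2:1 ratio to one of two treatment groups".

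The same SAP revision reports final enrolment in its Introduction: "There were 7 subjects enrolled under protocol version C, 5 enrolled under version E, 16 enrolled under version F, and 16 enrolled under version G", with none under versions D, H or I. SAP 10 cancels the interim analysis because the study stopped early. The primary test is left as it was, and neither its size nor its power is restated for the smaller trial. No unconditional exact test is named anywhere. SAP 9.4.1.1 asks for a 95% confidence interval for the rate difference without naming a method, whereas SAP 9.4.1.2.2 asks for an exact one in the mITT and PP analyses.

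**The concern.** Fisher's test conditions on the total number of responders, so its attainable significance levels are discrete. With 300 subjects the steps are fine and little alpha is lost. With 44 they are coarse, and the actual type I error can sit well below 0.05 whatever the common closure rate.

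Part of the alpha that the plan allows is then never used, in a trial that has already lost most of its power and cannot enrol more. The choice of test can also decide the single primary conclusion. At 29:15, a result of 16/29 (55%) v 3/15 (20%) lies inside the SAP's assumed ranges. Fisher's p is 0.052, not significant. Boschloo's test rejects, with maximum type I error still below 0.05.

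**Working it through.** **Inputs.** N = 7 + 5 + 16 + 16 = 44 (SAP 1). Two-sided alpha is 0.05 (SAP 4.1). Rates are p_t = 0.50, 0.55, 0.60 and p_c = 0.20, 0.25, 0.30 (SAP 6). Allocation is 2:1 (SAP 3), so 44 × 2/3 = 29.3, and 29:15 is the nearest split. The realised split is not in the documents, so 26:18 to 33:11 is taken as a range. Enrolled is taken to equal randomized.

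**Formulas.** Let F(x, y) be the two-sided Fisher p-value for x responders of n_t and y of n_c, defined as the sum over tables no more probable than the observed one.

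- Power(p_t, p_c) = Σ_x Σ_y Bin(x; n_t, p_t) · Bin(y; n_c, p_c) · 1[F(x, y) ≤ c], with c = 0.05 for Fisher's test.
- Maximum size = the largest value of Power(p, p) over the common rate p.
- Boschloo's test uses the same statistic F, but with the largest c whose maximum size is at most 0.05. Because c is at least 0.05, its rejection region contains Fisher's, so it cannot be less powerful.

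**Reproducing SAP Table 4 (200 v 100).**

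| p_t / p_c | SAP | Fisher as above | Fisher, doubled one-sided p |
|---|---|---|---|
| 0.50 / 0.30 | 0.898 | 0.918 | 0.897 |
| 0.50 / 0.25 | 0.985 | 0.990 | 0.986 |
| 0.55 / 0.30 | 0.982 | 0.986 | 0.982 |
| 0.60 / 0.30 | 0.998 | 0.999 | 0.998 |

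The table reproduces to within 2 points, and more closely with the doubled p-value. At 200:100 Fisher's maximum size is 0.046, so the planned conservatism was mild.

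**At 29:15.** Fisher's maximum size is 0.0347. Boschloo's is 0.0477, with c = 0.0588.

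| p_t / p_c | Fisher | Boschloo | Gain (points) |
|---|---|---|---|
| 0.50 / 0.20 | 0.409 | 0.493 | 8.4 |
| 0.50 / 0.25 | 0.268 | 0.351 | 8.2 |
| 0.50 / 0.30 | 0.165 | 0.234 | 6.9 |
| 0.55 / 0.20 | 0.520 | 0.622 | 10.2 |
| 0.55 / 0.25 | 0.369 | 0.475 | 10.5 |
| 0.55 / 0.30 | 0.248 | 0.341 | 9.3 |
| 0.60 / 0.20 | 0.638 | 0.739 | 10.0 |
| 0.60 / 0.25 | 0.493 | 0.604 | 11.1 |
| 0.60 / 0.30 | 0.362 | 0.468 | 10.6 |

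Gains are taken from unrounded powers.

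**Across splits**, over the same nine pairs:

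| Split | Fisher max size | Boschloo max size | Gain (points) |
|---|---|---|---|
| 26:18 | 0.0352 | 0.0494 | 5.2 to 7.1 |
| 27:17 | 0.0331 | 0.0488 | 6.4 to 9.6 |
| 28:16 | 0.0338 | 0.0483 | 5.8 to 8.8 |
| 29:15 | 0.0347 | 0.0477 | 6.9 to 11.1 |
| 30:14 | 0.0363 | 0.0484 | 6.2 to 9.2 |
| 31:13 | 0.0397 | 0.0481 | 1.3 to 3.3 |
| 32:12 | 0.0372 | 0.0464 | 0.4 to 1.7 |
| 33:11 | 0.0359 | 0.0491 | 1.3 to 3.1 |

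**Which two-sided p.** The SAP does not say which two-sided Fisher p-value it will use. The doubled version is more conservative still, with a maximum size of 0.023 at 29:15, so the tables above take the reading more favourable to the plan.

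**The case against.** The plan contains no mistake here. Fisher's test holds type I error at or below 0.05, it is the test on which both documents based power, and whether to condition on the total number of responders is a legitimate choice. A reader might infer that the SAP has mis-stated or failed to deliver its alpha. It has not: an upper limit of 0.05 is respected, and any conservative discrete test sits below its nominal level.

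A reader might also infer that 6 to 11 points of power are certainly being given up. The documents do not support that, because they give neither the realised split nor any block size. If allocation were simple 2:1 (an assumption), exactly 15 on placebo would have probability of only about 0.13, and 13 or fewer about 0.36. In that second region, down to 11 on placebo, the gain is about 0.4 to 3 points. Blocking would pull the split towards 29:15, but none is described.

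Nor would a different test rescue the trial. At 29:15 Boschloo's power still runs only from 0.23 to 0.74.

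Timing is the most practical objection. This revision already drops the confirmation visit from the primary endpoint and redefines the ITT, mITT and PP populations after enrolment ended. A further change to a test that rejects more often invites criticism, and the documents do not show that a blinded window remains. The primary test would also differ from the Fisher tests kept for the mITT and PP populations, the subgroups and 7-month closure.

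All of these points stand as limits on size and urgency. They do not remove the gain: Boschloo's test keeps exact size, cannot lose power, and can be presented with Fisher's test beside it.

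**Conclusion.** The point holds as a cheap improvement in efficiency, not as a validity error. At 44 subjects the primary Fisher test has maximum true size of about 0.033 to 0.040 against a permitted 0.05. Boschloo's test recovers 6.9 to 11.1 points of power at 29:15, about 5 to 10 points at 26:18 to 28:16 and at 30:14, and about 0.4 to 3 points at 31:13 to 33:11. The direction is the same at every split. Power is low either way: at 29:15 it is 0.17 to 0.64 for Fisher's test and 0.23 to 0.74 for Boschloo's.

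This rests on the 44 enrolled being the ITT population, on the SAP's own rate ranges, on a split within 26:18 to 33:11, and on the two-sided p-value defined by table probability.

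**What to change.** If the treatment codes are still masked:

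- In SAP 9.4.1.1, name Boschloo's exact unconditional test, two-sided at 0.05, as the primary test.
- Name the exact unconditional method for the 95% confidence interval of the rate difference, which currently has no stated method, and choose one compatible with the primary test.
- Report Fisher's test as supportive and state which two-sided p-value it uses. Say whether the mITT, PP, subgroup and 7-month analyses stay with Fisher's test.
- Record the date of the change and that it was made blind, with the early stop as the reason.
- Restate size and power for the realised sample.

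If unmasking has already happened, keep Fisher's test as primary and report Boschloo's only as a labelled supportive analysis.

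The cost is a paragraph of SAP text and a short program. The downsides are a less familiar test and a late change of the primary analysis that has to be defended.

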6. STATISTICAL METHODS

6.1. SAMPLE SIZE CALCULATION

The sample size for the primary efficacy endpoint is calculated based on the hypothesis for the primary efficacy endpoint. The primary study endpoint is the proportion of subjects with a target wound closure at 4 months.

The statistical hypotheses for the first primary efficacy endpoint are:

 H_0 : $P_t = P_c$ versus H_a : $P_t \neq P_c$

where P_t and P_c are the proportions of subjects with a target wound closure by the 4-month follow-up for the VM202 and placebo groups, respectively.

The hypothesis testing will be at two-sided 0.05.

Based on prior VM202 studies, the percentage of subjects achieving complete wound closure by the 4-month (i.e., 4-month responder rate) for VM202 (treatment arm) is assumed to range from 50% to 60%, and that for the Placebo group is assumed to range from 20% to 30%. Table 7 below summarizes the statistical power for a sample size of 200 VM202 and 100 Placebo subjects based on Fisher's exact test with a two-sided significance level of 0.05 for the statistical hypothesis.

Table 7. Statistical power by estimated responder rates for Treatment (p_t) and Control (p_c) arms

2100022020 (47) 0220 0022020 (46) 02220						
Pt	рc	Statistical Power				
0.50	0.20	>.999				
0.50	0.25	0.985				
0.50	0.30	0.898				
0.55	0.20	>.999				
0.55	0.25	0.999				
0.55	0.30	0.982				
0.60	0.20	>.999				
0.60	0.25	>.999				
0.60	0.30	0.998				

Except for the assumption of $p_t = 0.50$ and $p_c = 0.30$, the statistical power for all assumptions of p_t and p_c is > 0.95. For the assumption of $p_t = 0.50$ and $p_c = 0.30$, the statistical power is about 90%.

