5.4. Derived Variables

Baseline Value

The last non-missing value prior to first dose of study drug. If a subject does not receive any study drug, baseline is the latest recorded measurement on or before the randomization date.

Change from Baseline Value

Change from baseline value is the arithmetic difference between a value of interest and a baseline value: Change from baseline value = (value of interest – baseline value).

Percent Change from Baseline Value

The ratio of the arithmetic difference between a value of interest and the baseline value to the baseline value multiplied by 100: (Change from Baseline / Baseline) \times 100.

Time to Complete Wound Closure

Time to complete wound closure is the time interval (in days) from Day 0 to the date of the first visit date within the allowed visit window where wound closure is so indicated by the investigator. If a subject has not experienced complete wound closure, the subject will be considered censored at the subject's end of study date.

Time to a major amputation in the target limb

Time to a major amputation in the target limb is the time interval (in days) from Day 0 to the earliest date of a reported AE of an amputation of the lower extremity above the ankle of the target limb.

Time to a minor amputation in the target limb

Time to a minor amputation in the target limb is the time interval (in days) from Day 0 to the earliest date of a reported AE of an amputation of a foot or any parts of a foot such as toes on the target limb.

Absolute Differentials

If not provided by the individual study center labs, values for the absolute differentials (i.e., neutrophils, lymphocytes, monocytes, eosinophils, and basophils) will be calculated by multiplying the WBC count by the corresponding percent differential in the total WBC count. Results should be rounded to the nearest hundred for units equivalent to $10^3/\mu L$.

Percent Differentials

If not provided by the individual study center labs, values for the percent differential (i.e., neutrophils, lymphocytes, monocytes, eosinophils, and basophils) will be calculated by dividing the corresponding absolute differential count by the total WBC count. Results should be rounded to the tenth of a percentage point.

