8.2. Visit Windows

Data at each scheduled follow-up visit will be analyzed according to the nominal visit identified on the data record. In case of multiple different visits identified with the same nominal visit, the visit with the visit date closest to the target days of each protocol-specified visit schedule (Table 5) will be used for the efficacy analyses of exploratory endpoints assessed at specific months. For visits with the same distance to the target days, the later nominal visit record will be used. Data from the other visits (if any) will be provided in data listings.

Table 5 Target Day and Month Descriptor

	1 st INJECTION	2 ND INJECTION	3 RD INJECTION	4 TH INJECTION	DAY 60	DAY 74	DAY 90	DAY 120	DAY 210
TARGET DAY	0	14	28	42	60	74	90	120	210
FOLLOW-UP MONTH	-	-	-	-	2	2.5	3	4	7

Data from 'weekly wound assessment and dressing change', 'confirmation of ulcer healing', 'early withdrawal', and any unscheduled study visits will be used in addition to the scheduled target day visits to determine efficacy endpoints that are the response rate by a given follow-up visit (e.g., the primary efficacy endpoint) or a time to event endpoint (e.g., time to complete wound closure).

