9.4. Efficacy Endpoint Analyses

9.4.1. Primary Efficacy Endpoint

The primary efficacy endpoint is the proportion of subjects with a target wound closure by the 4-month follow-up (responder). The responder rate will be compared between the two treatment groups (VM202 and placebo).

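### The missing-status sentence in SAP 9.4.1.1, read literally, scores a documented closer who leaves before the 4-month visit as a non-responder, against the plan's own definition of response

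*SAP*

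**What the plan says.** SAP 4.1 sets the endpoint: "The primary efficacy endpoint is the proportion of subjects with a target wound closure by the 4-month follow-up". SAP 9.4.1 repeats it as the definition of a responder, and Protocol 6.3.1 also uses by. SAP 1, describing the change made with protocol version I, says the endpoint now takes in every subject with closure by that visit and no longer needs confirmation. SAP 5.3.2 allows closure at any time during the study.

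SAP 8.2 says which visits feed the endpoint: "Data from 'weekly wound assessment and dressing change', 'confirmation of ulcer healing', 'early withdrawal', and any unscheduled study visits will be used". These sources come on top of the scheduled visits, and 8.2 names the primary endpoint as its example of a response rate by a given visit.

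SAP 9.4.1.1, on the primary analysis, then says: "Subjects whose status of wound closure cannot be assessed at 4 months (e.g., due to earlier discontinuation from the study), will be considered non-responders". It makes no exception for a closure already recorded.

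Protocol 6.1 uses both prepositions. It opens with "The primary study endpoint is the proportion of subjects with a target wound closure at 4 months", and its hypotheses then speak of closure by the 4-month follow-up.

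**The concern.** Take a subject whose ulcer is recorded as closed on Day 60 and who leaves the study on Day 80. Response by 4 months has been observed, yet status at 4 months has not, and earlier discontinuation is the very example that 9.4.1.1 gives. A programmer who applies that sentence as written sets the flag to non-responder. One who works from 4.1 and 8.2 sets it to responder. No passage says which text prevails.

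The flag drives the only confirmatory comparison. SAP 8.4 forgoes a multiplicity adjustment because there is one endpoint, one population and one analysis method; that argument is cleanest when the flag has one derivation. No planned analysis would show the effect of the rule: SAP 9.1 announces sensitivity analyses with other ways of handling missing data, but 9.4.1.2 lists only a logistic model and other populations. The exploratory time to closure would count the same subject as an event, dated at "the first visit date within the allowed visit window where wound closure is so indicated by the investigator", so the two endpoints could disagree because of wording alone.

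**Working it through.** **1. The passages applied to one subject (closed Day 60, leaves Day 80)**

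| Place | What decides | Result |
|---|---|---|
| SAP 4.1, 9.4.1; Protocol 6.3.1 | closure by the 4-month follow-up | responder |
| SAP 1, version I change | every subject with closure by then | responder |
| SAP 5.3.2 | closure at any time in the study | closure counts |
| SAP 8.2 | weekly, confirmation, early-withdrawal, unscheduled visits used | responder |
| SAP 9.4.1.1, literal | status assessable at 4 months | non-responder |

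Under the literal rule, an early-withdrawal visit before 4 months could never establish a primary response, although 8.2 lists such visits as a source for it. SAP 3 also has subjects attend "once a week for dressing changes and wound assessment until the ulcer has healed or study exit, whichever comes first", and ulcer measurement stops at closure. The plan therefore treats a recorded closure as settling the matter.

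**2. The plan's own figure.** SAP Table 4 gives power 0.898 for 200 v 100 at 0.50 v 0.30 (Fisher's exact test, two-sided 0.05). Full enumeration gives 0.918. A continuity-corrected normal approximation gives the stated value: pooled rate (200×0.50 + 100×0.30)/300 = 0.433; null SE √(0.433×0.567×0.015) = 0.0607; alternative SE √(0.25/200 + 0.21/100) = 0.0579; z = (0.20 − 0.0075 − 1.96×0.0607)/0.0579 = 1.27; power 0.898. The sample-size figure is not in dispute.

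**3. Inputs for the size of the problem**
- Enrolled: 7 + 5 + 16 + 16 = 44 (SAP 1), taken as the ITT set.
- Arm split: not given; 28/16, 29/15 and 30/14 assumed from 2:1.
- Closure rates: 0.50, 0.55, 0.60 (VM202) and 0.20, 0.25, 0.30 (placebo), from SAP Table 4.
- q, the share of closers who leave after closure and before the 4-month visit: not given; 2%, 5% and 10% assumed, equal in both arms.
- Significance means two-sided Fisher p<0.05 in favour of VM202. Power with 44 subjects is 0.16-0.69.

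**4. Weight of one subject.** One recoded closer moves the VM202 rate by 1/30 to 1/28 (3.3-3.6 points) or the placebo rate by 1/16 to 1/14 (6.3-7.1 points). Illustrations at 29/15, not trial data: 17 v 3 closers gives p=0.025 and 16 v 3 gives p=0.052; 15 v 3 gives p=0.057 and 15 v 2 gives p=0.021.

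**5. How often the readings disagree.** In each arm, documented closers a ~ Bin(n, p) and closers kept by the literal rule a′ ~ Bin(a, 1−q), independently by arm. The probability that the two verdicts differ is summed over all tables. The probability that nobody is recoded is (1−q·p_t)^n_t × (1−q·p_c)^n_c. For example, at q=2%, 28/16 and 0.50 v 0.20: 0.99^28 × 0.996^16 = 0.71.

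| q, both arms | Significance lost | Gained | Readings disagree | Nobody recoded |
|---|---|---|---|---|
| 2% | 1.3-2.9% | 0.9-1.4% | 2.2-4.1% | 64-71% |
| 5% | 2.8-6.5% | 2.0-2.7% | 4.7-8.9% | 32-42% |
| 10% | 4.6-11.1% | 2.8-3.9% | 7.7-14.7% | 10-17% |

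Lost and gained means going from the responder reading to the literal one; ranges run over splits and rates. At q=10% in VM202 only, significance is lost in 5.8-14.7% of trials; at q=10% in placebo only, it is gained in 5.7-8.5%.

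**6. Given exactly one recode.** The affected arm must hold at least one closer, so its count is 1 + Bin(n−1, p) (small-q limit). Significance is then lost in about 5-9% of trials if the recoded closer is on VM202, or gained in about 11-22% if on placebo.

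**The case against.** The best defence is that 9.4.1.1 is a missing-data rule. It bites only where closure status cannot be assessed, and for a subject with closure on record that status is known. The example of earlier discontinuation illustrates why status may be unknown; it need not mean that every leaver is unassessable. The rest of the SAP points the same way, and the stray at in Protocol 6.1 sits beside a by in the same section. All of this stands as to intent. It does not remove the defect, because the exception it needs is not written in the sentence that scores the primary endpoint.

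Three stronger readings are tempting, and the documents support none of them:
- **That the two derivations have equal standing.** They do not; the weight of the SAP is with the responder reading.
- **That subjects have been or will be misclassified, or that the rule favours VM202.** No count of early-leaving closers is given, and the direction depends on which arm they are in.
- **That the wording would be chosen after the results are seen.** Nothing suggests this. Settling it beforehand simply closes the possibility.

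It is also fair to say that the study stopped early and has low power at 44 subjects, so the practical stake is limited.

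**Conclusion.** The point holds as a wording conflict. One sentence in SAP 9.4.1.1, applied literally, gives a flag that contradicts the endpoint it is meant to score. Under the responder reading nothing else in the plan is disturbed.

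The effect on the result could be nil. Across assumed early-leaving shares of 2-10% in both arms, the readings disagree on significance in roughly 2-15% of trials; with no early-leaving closers they never disagree. These figures rest on the assumed shares, the assumed arm split, the SAP's planning rates and the 44 enrolled subjects being the ITT set. The figures conditional on one recode are not probabilities that the ambiguity changes the result.

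Grade: minor to should-fix, because the sentence governs the only confirmatory test and is cheap to repair.

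**What to change.** Before the randomization code is unmasked, replace the sentence in SAP 9.4.1.1 with:

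> A subject with complete closure documented at any scheduled, weekly, confirmation, early-withdrawal or unscheduled visit up to and including the 4-month follow-up is a responder, regardless of later discontinuation; subjects with no documented closure by then, including those who discontinue earlier, are non-responders.

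If the literal rule was intended, SAP 4.1, 8.2 and 9.4.1 and Protocol 6.3.1 must change instead. Either way, use by the 4-month follow-up consistently in Protocol 6.1 if that is what is meant.

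The cost is one sentence, with no new visit, procedure or data. The same flag feeds the logistic model, the mITT and per-protocol analyses, the subgroup analyses and the covariate model (SAP 9.4.1.2 to 9.4.3), so all must be run from the one derivation. An ulcer that closes and reopens before 4 months counts as a response under this wording, as it already does under the current definition, which no longer requires confirmation; that is a separate question and is not altered here.
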